9.3.2 Outcomes

9.3.2.1 Primary outcomes

Safety outcomes:

- Percentage of subjects with adverse drug reactions (ADRs) by severity class

Effectiveness outcomes:

- Time on treatment with Gi(1)otrif[®]
- Time to progression with Gi(1)otrif[®]

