9.7 DATA ANALYSIS

9.7.1 Main analysis

All collected data will be analysed separately for patients starting with 40mg and \leq 30mg. Although due to anticipated low sample size in patients starting with \leq 30mg, it will be mainly for exploratory purpose. Baseline demographics will be analysed with descriptive statistics (N, median, mean, 25%, 75% percentile, SD) and compared descriptively between patients who have dose modifications within the first 6 months of Gi(l)otrif[®] treatment and those who do not. All the demographics, safety and efficacy data from this study in real-world setting will be compared with data from LUX-Lung 3 trial in descriptive manner.

Analysis of Safety:

[figure not shown]
Safety analysis will include all patients treated with Gi(l)otrif[®] and be descriptive in nature. Incidence and severity of ADRs according to Common Terminology Criteria for Adverse Events (CTCAE) criteria (version 4.0) ([R15-5988](#)) when available will be summarized and displayed in number/percentage. For patients who had Gi(l)otrif[®] dose modifications within the first 6 months of Gi(l)otrif[®] treatment, frequency and severity of the common ADRs pre- and post-dose modification will be analysed (\geq 40mg vs $<$ 40mg; and \geq 30mg vs $<$ 30mg). Missing or incomplete ADR dates will be imputed according to BI internal SOPs.

Analysis of Effectiveness:

Effectiveness analysis will include all patients treated with Gi(l)otrif[®]. Time on treatment is from the date of first dose of Gi(l)otrif[®] treatment to the date of last dose of Gi(l)otrif[®] treatment. Time to progression is from the date of first dose of Gi(l)otrif[®] treatment to the earliest date of documented progression (clinical, radiographic or both clinical/radiographic progression) or death. Time on treatment and time to progression will be estimated using Kaplan-Meier method, and the median along with two-sided 95% CI will be displayed (use the Greenwood's formula for estimation of standard errors). Log-rank test will be applied to compare between patients with and without dose modifications. Time on treatment and time to progression will be compared between patients who dose reduced to $<$ 40 mg within the first 6 months of Gi(l)otrif[®] treatment and those who remained on Gi(l)otrif[®] 40 mg once daily. This is in analogy to the analysis made on LUX-Lung 3 where a cut-off of 6 months was used as most dose reductions occur during this time.

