In the analyses of the two time-to-event endpoints, missing or incomplete data are managed by standard survival analysis techniques. For patients still on treatment, time on treatment will be censored at the date of data collection. For patients still on treatment and without progression, time to progression will be censored at the date of data collection. For patients stopped treatment and without progression/death or progression/death date missing, time to

progression will be censored on the last contact date.

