## 1 Methods for calculation of derived variables

Age at registration: Year of registration [patient.birthyear] – Year of birth [registration.registered\_at]

Drug-related AE: All AE with relationship to Gi(I)otrif® [ae.gilotref\_relation\_1='yes']

Time on treatment: Date of last administration [endofobservation.date] - Date of first administration of Gi(I)otrif® [baseline.date]. For patients still on treatment, time on treatment will be censored at the date of data collection.

Time to progression (TTP): First date of progression [min(endofobservation.radio\_date, endofobservation.clinic\_date)] - Date of first administration of Gi(I)otrif® [baseline.date]. Patients not known to have a progression will be censored with the date of last contact. For patients still on treatment and without progression, time to progression will be censored at the date of data collection. For patients who stopped treatment and without progression or progression date missing, time to progression will be censored on the last contact date.

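### The SAP leaves death out of the time-to-progression event and censoring rules, although the protocol counts it as an event in this primary outcome

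*SAP*

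**What the plan says.** Protocol section 9.3.2.1 lists "Time to progression with Gi(1)otrif" as a primary effectiveness outcome. Section 9.7.1 measures it from first dose "to the earliest date of documented progression (clinical, radiographic or both clinical/radiographic progression) or death". For patients off treatment, the same section censors at last contact under this condition: "For patients stopped treatment and without progression/death or progression/death date missing". The two time-to-event outcomes are summarised by Kaplan-Meier medians with confidence intervals, and "Log-rank test will be applied to compare between patients with and without dose modifications". Section 9.7.1 also states that "efficacy data from this study in real-world setting will be compared with data from LUX-Lung 3 trial", descriptively.

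SAP section 1 starts its derivation with "Time to progression (TTP): First date of progression" and computes this as the earlier of the radiographic and clinical progression date fields, minus first administration. A general rule follows: "Patients not known to have a progression will be censored with the date of last contact". The rule for patients off treatment is "For patients who stopped treatment and without progression or progression date missing, time to progression will be censored on the last contact date". Death appears nowhere in the SAP text supplied.

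**The concern.** The two documents give different event definitions for one primary outcome. The SAP says that its field references tell the programmer where to find each parameter, so its formula would be coded as it stands. Patients who die without recorded progression would then leave the event count and be treated as non-informatively censored.

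Two comparisons are exposed. The first is with LUX-Lung 3. The only progression endpoint that the protocol reports for that trial (section 7) is PFS, which in its usual meaning counts death, and section 9.7.1 says that the dose-reduction contrast is made by analogy with the LUX-Lung 3 analysis. The second is the log-rank test between patients with and without dose modification. It loses events in any case, and it changes in value if early deaths are distributed differently between the groups.

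**Working it through.** **Text comparison**

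| Element | Protocol 9.7.1 | SAP section 1 |
|---|---|---|
| Event | Progression or death, whichever is earlier | Radiographic or clinical progression, whichever is earlier |
| Off treatment, censored if | Neither progression nor death, or the date is missing | No progression, or the progression date is missing |
| General rule | None | Everyone without known progression is censored at last contact |
| On treatment without progression | Date of data collection | Same |

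A death without recorded progression is classified differently in the first two rows, and the SAP's general rule leaves no route by which it could become an event.

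**Size.** The documents give no event count, power or alpha for this outcome, so there is no planned figure to reproduce. Let q be the share of first events that are deaths without recorded progression. It is not in the documents; the range 2% to 20% is assumed. With constant hazards and last contact on the day of death, censoring these deaths multiplies the event hazard by (1 − q). Hence:

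- median = m / (1 − q)
- 12-month event-free probability = exp(−ln 2 × (1 − q) × 12 / m)
- standard error of the log hazard ratio rises by the factor 1/√(1 − q), if q is equal in both groups

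For m, take the two LUX-Lung 3 afatinib medians in protocol section 7: 11.1 months (all patients) and 13.6 months (the common mutations, which match this study's eligibility). With m = 13.6 and q = 0 the 12-month probability is 54.2%.

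| q | Median from 11.1 | Median from 13.6 | 12-month probability, m = 13.6 | Rise in standard error |
|---|---|---|---|---|
| 2% | 11.3 | 13.9 | 54.9% | 1.0% |
| 5% | 11.7 | 14.3 | 55.9% | 2.6% |
| 10% | 12.3 | 15.1 | 57.7% | 5.4% |
| 15% | 13.1 | 16.0 | 59.5% | 8.5% |
| 20% | 13.9 | 17.0 | 61.3% | 11.8% |

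Example: 13.6 / (1 − 0.10) = 15.1. The same formula moves the 11.0-month median reported for LUX-Lung 3 patients without early dose reduction to 11.6 at q = 5% and 12.2 at q = 10%.

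**Last contact before death.** In a simulation of 400,000 patients (m = 13.6, censoring assumed uniform over 6 to 36 months), last contact 6 months before death gives a median of 14.7 at q = 10% and 16.1 at q = 20%. The shift shrinks but remains.

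**Direction.** It is upward for certain when last contact is the death date, but not in every data set otherwise. Take three patients: one last seen at month 10 who dies at month 14, and two who progress at months 12 and 20. The protocol rule gives S(12) = 2/3 and a median of 14; the SAP rule gives S(12) = 1/2 and a median of 12. In 3,000 simulated samples of 200 patients per setting (q of 2% to 20%, last contact 0, 3 or 6 months before death), the SAP median fell below the protocol median in at most 1.2%.

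**Sampling error.** With 200 patients and the same assumed censoring, the 95% sampling range of the median is about 9.0 to 13.5 months (true value 11.1) or 11.0 to 16.8 (true value 13.6).

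**Unequal shares between dose groups.** Apparent hazard ratio = true hazard ratio × (1 − q1)/(1 − q0). With a true ratio of 1.00:

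- 10% against 5% gives 0.90/0.95 = 0.95
- 15% against 5% gives 0.85/0.95 = 0.89
- 5% against 15% gives 0.95/0.85 = 1.12

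**The case against.** Several points can be made for the plan.

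- **Size is assumed.** Correct. Protocol section 9.9 expects most patients to be alive and notes that data on deceased patients are restricted in some countries, so q may be low. At 2% to 5% the shift of 0.2 to 0.7 months is well inside sampling error. But that expectation concerns overall survival and does not bound q, and sampling error does not excuse an avoidable systematic difference.
- **The study is descriptive.** No formal hypothesis is stated, and the protocol does not say in so many words that time to progression will be set beside PFS. The link rests on the stated analogy with LUX-Lung 3 and on PFS being the only progression endpoint reported for it. Descriptive medians still need matching definitions.
- **No hazard ratio is planned.** True; the ratios above only summarise how the log-rank contrast would move. Censoring deaths also targets a legitimate quantity, the progression-specific hazard. It is not the one that the protocol defines.
- **The death date may not be available.** This one has weight. Section 9.3 lists no date of death and stops documentation at last dose, and section 11.2 collects fatal adverse events only from consent onwards, which may miss earlier deaths in a chart review. But the protocol's own definition already presupposes a death date.
- **The SAP is supplied only in part.** The finding therefore concerns its derivation section as written; that section is a complete rule, and nothing else supplied overrides it.

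**Conclusion.** The concern holds. A primary outcome has two incompatible event and censoring rules, and neither document explains the change. This rests on the text alone and must be settled before analysis.

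The SAP rule departs from the protocol definition almost always in the direction of a longer time to progression. How far is unknown: for assumed q of 2% to 20% and constant hazards the median rises by 0.3 to 3.4 months from 13.6, or by 0.2 to 2.8 from 11.1, and by less if last contact precedes death. Whether the dose-group contrast changes in value, beyond losing precision, depends on whether q differs between the groups, which cannot be judged from the documents.

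**What to change.** In SAP section 1:

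1. Define the event date as the earliest of radiographic progression, clinical progression and death, and name the eCRF field for death.
2. Reword the general rule so that it censors only patients not known to have progressed or died.
3. Restore death in both places of the off-treatment rule. The on-treatment rule already agrees with the protocol, and needs a change only if it can include a patient who has died.

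If a death-censored outcome is really intended, amend and justify protocol section 9.7.1 instead, and do not present the result as like for like with LUX-Lung 3 PFS.

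In either case, confirm that the eCRF, which was not among the documents reviewed, holds dates of death and last contact, including for deaths before consent. Reconcile the data window in section 9.3 (to last dose) with section 9.7.1 (last contact after stopping), section 9.10.4 (to end of data collection) and section 11.2 (fatal events to end of study).

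Cost: the SAP text needs one added term and two edited sentences. If the death date is not already captured, there is extra chart abstraction. Changing the section 9.3 window or the protocol definition is an amendment that needs ethics committee and authority approval (section 10.1.1) in up to 13 countries. The reported median will usually be somewhat less favourable.

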9.3 VARIABLES

Data will be documented from the date of first dose of Gi(l)otrif[®] treatment until the date of last dose of Gi(l)otrif[®] treatment or end of data collection whichever occurs first.

During the data collection period, the following data will be collected from medical records in an eCRF by investigators during the study:

- Informed consent
- Diagnosis
- Demographics (gender, date of birth, ethnicity)
- Body weight and height at start of Gi(l)otrif[®] treatment
- ECOG performance score at start of Gi(l)otrif[®] treatment
- EGFR mutational subgroup (Del19/L858R)
- Starting dose of Gi(l)otrif[®]
- Start date of Gi(l)otrif[®] treatment
- End date of Gi(l)otrif[®] treatment
- Gi(l)otrif[®] dose modification(s) and date(s)
- ADRs
- Concomitant medications (limited to medication for management of diarrhea, skin effects, mucositis/stomatitis as dichotomous variables (e.g. received anti-diarrhea medication yes/no))
- Reason for dose modification(s)
- Date of progression
- Type of progression:
 - a. clinical
 - b. radiographic
 - c. both clinical/radiographic progression

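### Time to progression after stopping is censored at last contact, but later anticancer therapy is not listed for collection and documentation ends at last dose, so off-drug time enters with a bias of unknown direction

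*SAP*

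**What the plan says.** Protocol 9.3.2.1 names "Time to progression with Gi(1)otrif" as a primary effectiveness outcome, beside time on treatment. Under 9.7.1 the event is the "earliest date of documented progression (clinical, radiographic or both clinical/radiographic progression) or death", with no restriction to the period on drug.

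For patients who have stopped, the sentence in 9.7.1 that begins "For patients stopped treatment and without progression/death or progression/death date missing, time to" goes on to censor at last contact. SAP section 1 gives a general rule, "Patients not known to have a progression will be censored with the date of last contact", and then the specific one: "For patients who stopped treatment and without progression or progression date missing, time to progression will be censored on the last contact date". Neither document censors at last dose or at the start of another therapy.

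On collection, Protocol 9.3 documents data from the first dose "until the date of last dose of Gi(l)otrif[®] treatment or end of data collection whichever occurs first". Other treatment is restricted to "Concomitant medications (limited to medication for management of diarrhea, skin effects, mucositis/stomatitis as dichotomous variables". No item for later anticancer therapy appears in 9.3 or in the parallel list in 9.1. The start and end dates of afatinib and the date of progression are listed; last contact date and death are not.

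Patients who stopped before 6 months are deliberately included (9.2.1). Time to progression is compared by log-rank test between patients with and without dose modification, and specifically between those reduced below 40 mg within 6 months and those who stayed on 40 mg (9.7.1). The sections on limitations (9.9) and bias (9.12) do not mention treatment after afatinib.

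**The concern.** A patient who stops for toxicity before progressing keeps contributing to time to progression until progression, death or last contact. Part of that time may be spent on another anticancer drug. With no record of that drug or its start date, the report cannot say how much of the follow-up it covers, and no analysis can be censored at the switch.

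This matters because the dose-group comparison is what the study sets beside LUX-Lung 3, where outcomes were described as similar with and without reduction (Protocol 7). A similarity or difference that partly reflects later treatment would be read as an effect of afatinib dose.

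The 9.3 window adds a second problem. If progression is documented only up to last dose while the time axis runs to last contact, stoppers carry event-free time in which no event could have been recorded.

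**Working it through.** **No stated figure to reproduce.** The study size rests on feasibility and similarity to the 229 patients of the LUX-Lung 3 analysis. The documents give no share of patients stopping without progression, overall or by dose group.

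**Passages side by side**

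- The event and censoring rules (Protocol 9.7.1, SAP 1) need information after last dose: progression, death, last contact.
- Protocol 9.3 closes documentation at last dose. Protocol 9.10.4, by contrast, continues collection to the end of data collection or withdrawal of consent, so the protocol does not settle the question.
- The protocol counts death as an event; the SAP derivation uses progression dates only.

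**Illustration of direction and size, single group**

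Inputs:

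- On-drug median 11.1 months, the LUX-Lung 3 afatinib median PFS (Protocol 7), taken as exponential (assumption).
- A share f of patients is assigned a stop, uniform over months 0 to 6; f = 5% to 30% (assumption).
- Median m from stopping to progression: 6.9 months (LUX-Lung 3 chemotherapy PFS, used only as a scale), 11.1, or 16.65 = 1.5 × 11.1 (assumptions).

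Let h = ln 2/11.1 = 0.06245 and g = ln 2/m. For t > 6:

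- Later progressions recorded: S(t) = (1 − f)·e^(−ht) + f·c·e^(−gt), with c = (e^(6(g−h)) − 1)/(6(g−h)), and c = 1 if g = h.
- Later progressions not recorded, time running on to last contact: S(t) = (1 − f)·e^(−ht) + f·a, with a = (1 − e^(−6h))/(6h) = 0.834.
- Censored at last dose: the median stays at 11.1 for every f, because stopping is assumed independent of progression.

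The median solves S(t) = 0.5. Two examples at f = 20%:

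- m = 6.9: g = 0.10046, c = 1.1232. At t = 10.31, 0.8 × 0.5253 + 0.2 × 1.1232 × 0.3550 = 0.4202 + 0.0797 ≈ 0.50.
- Not recorded: e^(−ht) = (0.5 − 0.2 × 0.834)/0.8 = 0.4165, so t = 0.8759/0.06245 = 14.03.

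| Assigned to stop (f) | Stop before progressing (0.834·f) | Recorded, m = 6.9 | Recorded, m = 11.1 | Recorded, m = 16.65 | Not recorded |
|---|---|---|---|---|---|
| 5% | 4.2% | 10.89 | 11.10 | 11.25 | 11.67 |
| 10% | 8.3% | 10.69 | 11.10 | 11.40 | 12.34 |
| 20% | 16.7% | 10.31 | 11.10 | 11.73 | 14.03 |
| 30% | 25.0% | 9.95 | 11.10 | 12.07 | 16.50 |

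A simulation of 400,000 patients with the data cut uniform over 6 to 36 months (assumption) gave the same medians to within 0.05 month.

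**Between groups.** The effect on the dose comparison depends on the stopping share and later treatment in each group. The documents give neither, so it cannot be computed.

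**The case against.** Following patients to progression whatever they receive next is a legitimate strategy, and it avoids informative censoring at a toxicity stop. Start and end dates of afatinib are collected, so off-drug time can be identified for anyone with a known last contact, and an analysis censored at last dose needs no new field. Time on treatment already reports drug-specific duration, and the study is largely descriptive. The list in 9.3 is also not exhaustive: it omits death and last contact, which the analysis uses, and fatal adverse events are collected under 11.2. The eCRF is not among the documents.

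Most of this stands. It is why the planned analysis should be kept, and why the point is that later therapy is not listed, not that it is certainly not collected. What remains is that the agent and its start date are unavailable on the protocol's list, that the strategy is not stated and sits badly with the outcome's name, and that 9.3 does not support the censoring date.

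A reader might go further and infer that progression-free time on another drug is credited to afatinib, mainly in patients who stopped without reducing. The documents do not support that. A later progression also counts against afatinib, so the median can fall. Patients who reduced can also stop and switch. It is also unclear whether someone who stopped at month 2 without reducing belongs to the group that stayed on 40 mg.

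**Conclusion.** The point holds in a limited form. Off-drug time, possibly on another agent, can enter time to progression and its comparison by dose reduction. The treatment given in that time cannot be described from the listed data. The direction of the bias and its split between groups are unknown.

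Under the stated assumptions, the single-group median moves by −1.1 to +1.0 months from 11.1 when later progressions are recorded, and not at all if the next treatment controls disease equally long. The clear inflation, +0.6 to +5.4 months, needs later progressions to go unrecorded while time runs well past last dose. A strict reading of 9.3 allows this but does not establish it, and it shrinks as last contact approaches last dose. These are illustrations, not study estimates, and say nothing about the between-group difference.

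The point warrants a change before data collection, but it does not invalidate the planned analysis.

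**What to change.** 1. Reconcile the documentation window in Protocol 9.3 with the censoring rules in 9.7.1 and SAP 1, so that progression, death and last contact date are collected after last dose. Align the SAP with the protocol on death as an event.
2. Add to the eCRF the start date and type of the first subsequent systemic anticancer therapy.
3. Keep the planned analysis and state that it follows patients regardless of later treatment. Prespecify in 9.7.1 and the SAP two supportive analyses of time to progression: one censored at the start of subsequent therapy, and one censored at last dose, which uses dates already listed.
4. Report by dose group how many patients stopped, and how many switched, before progression. If the analyses disagree, do not attribute the comparison to dose.

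The cost is one further field from the same chart, completed entries after last dose, and two more Kaplan-Meier analyses. Censoring at a switch or at last dose may itself be informative, so both stay supportive. Protocol 9.10.5 allows no further data after completion, so the field is hard to add later.

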7. RATIONALE AND BACKGROUND

The first marketing approval of afatinib was granted on 12 Jul 2013 in the USA (trade name Gilotrif[®]) for the indication of first-line treatment of patients with metastatic non-small cell lung cancer (NSCLC) whose tumors have epidermal growth factor receptor (EGFR) exon 19 deletions or exon 21 (L858R) substitution mutations as detected by an FDA-approved test. It was approved in the European Union on 25 Sep 2013 (trade name Giotrif[®]) as monotherapy indicated for the treatment of EGFR TKI-naïve adult patients with locally advanced or metastatic NSCLC with activating EGFR mutation(s). [REDACTED]

The approval of Giotrif[®] was based on the results observed in the pivotal trial LUX-Lung 3 study. The LUX-Lung 3 study investigated the efficacy of chemotherapy compared with afatinib, a selective, orally bioavailable ErbB family blocker that irreversibly blocks signaling from epidermal growth factor receptor (EGFR/ErbB1), human epidermal growth factor receptor 2 (HER2/ErbB2), and ErbB4 and has wide-spectrum preclinical activity against EGFR mutations. A total of 1,269 patients were screened, and 345 were randomly assigned to treatment (afatinib or chemotherapy). Median progression-free survival (PFS) was 11.1 months for afatinib and 6.9 months for chemotherapy (hazard ratio [HR], 0.58; 95% CI, 0.43 to 0.78; P=.001). Median PFS among those with exon 19 deletions and L858R EGFR mutations (n=308) was 13.6 months for afatinib and 6.9 months for chemotherapy (HR, 0.47; 95% CI, 0.34 to 0.65; P=.001). The most common treatment related adverse events were diarrhea, rash/acne, and stomatitis for afatinib and nausea, fatigue, and decreased appetite for chemotherapy. Patients reported outcomes (PROs) favored afatinib, with better control of cough, dyspnea, and pain ([P13-07382](#)).

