9.9 LIMITATIONS OF THE RESEARCH METHODS

The generalization and consequently the external validity of the study results, may be limited by the participation in the study of only sites that prescribe Gi(l)otrif[®] on a regular basis to ensure sufficient patient recruitment. Patients treated by investigators with less experience might experience more side effects during their treatment with Gi(l)otrif[®].

Methodological efforts have been taken to minimize selection bias: these efforts include the recommendation to include consecutive patients meeting each of the inclusion criteria and none of the exclusion criteria. In addition, this possible selection bias may be limited by the retrospective aspect of the data collection, data that have been already collected at the time of the study. Linked to this aspect is then the limitation due to data availability. Indeed, no additional data will be collected for the study purpose. So if the data is not available in the patient files, then this will be considered as missing data.

In addition, to reduce error in data collection, a standard study eCRF will be used, ensuring a measure of consistency among the collectors.

Another limitation is coming from the diverse handling of data collection from deceased patients which is allowed without informed consent in some countries but not in all.

However, no country-based analyses will be done. Given the median overall survival (31.6 months in LUX-Lung 3) and that time from launch of Gi(l)otrif to data collection in the participating countries is shorter than the median overall survival (OS) the majority of the patients are expected to be alive.

External validity is provided by the global approach of this study and the broad inclusion criteria but limited to patients treated within the label and at the selected, experienced sites. Internal validity will be given by source data verification.

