### Missing / Incomplete AE Onset Dates:

For each missing / incomplete AE onset date, an interval (INT\_START, INT\_END) is defined. The true unknown analysis start date of the AE is assumed to be within this interval. If the AE onset date is completely missing INT\_START will be Min(AE end date, Date of informed consent) and INT\_END will be Min(AE end date, Date of last visit). If only the year of the AE onset date is non-missing INT\_START will be Min(AE end date, 01 JAN of the reported year) and INT\_END will be Min(AE end date, 31 DEC of the reported year). If only year and month of the AE onset date are non-missing INT\_START will be Min(AE end date, 01 of the reported month) and INT\_END will be Min(AE end date, Last date of the reported month). Completely missing AE end date will not be considered in this derivation step. Partially missing AE end date (i.e., year and month are non-missing or only year is non-missing) will be temporarily assigned the largest possible date in the observed year or month and year in this derivation step. After this the imputed AE onset dates will be derived based on the intervals (INT\_START, INT\_END). If the date of first drug administration is within the interval [INT\_START, INT\_END] then the imputed AE onset date will be the date of drug administration. If the date of first drug administration is before INT\_START then the imputed AE onset date will equal INT\_START. If the date of first drug administration is after INT\_END or missing then the imputed AE onset date equals INT\_END.

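### Patients with recorded but undated progression are censored at last contact, which discards known events and biases the time-to-progression median upward

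*SAP*

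**What the plan says.** SAP section 1 measures time to progression from first dose to the earlier of the radiographic and clinical progression dates. It then gives censoring rules. One covers patients without known progression: "Patients not known to have a progression will be censored with the date of last contact". Another reads: "For patients who stopped treatment and without progression or progression date missing, time to progression will be censored on the last contact date". Since the first sentence already deals with patients who have no known progression, the missing-date clause must also apply to patients with progression on record and no date.

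Protocol section 9.7.1 has a parallel sentence, "For patients stopped treatment and without progression/death or progression/death date missing, time to" progression, which sends these patients to censoring at last contact. The protocol counts death as an event and so includes an undated death. The SAP's definition of time to progression does not mention death.

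The protocol describes its general approach as follows: "In the analyses of the two time-to-event endpoints, missing or incomplete data are managed by standard survival analysis techniques". Section 9.9 accepts gaps in the charts: "So if the data is not available in the patient files, then this will be considered as missing data". The only date-imputation rule is for adverse event onset in the SAP ("For each missing / incomplete AE onset date, an interval" is defined). Neither document gives an imputation rule, an interval-censored analysis, a sensitivity analysis or a count of affected patients for progression dates.

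**The concern.** Right-censoring says that the event had not happened by the censoring time. For a patient with recorded progression that is known to be false: the event occurred at or before last contact and only its date is unknown. The rule does two things. It removes the event, and it keeps the patient in the risk set, progression-free, for any time between progression and last contact. Both push the Kaplan-Meier curve up.

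Time to progression is a primary effectiveness outcome (protocol section 9.3.2.1). Its median is to be set beside LUX-Lung 3, where "Median progression-free survival (PFS) was 11.1 months for afatinib and 6.9 months for chemotherapy". It also enters the between-group test: "Log-rank test will be applied to compare between patients with and without dose modifications". Missing dates are foreseeable in a chart review that collects nothing new, and the plan foresees them by writing a rule.

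**Working it through.** No figure in the plan depends on this rule, so there is none to reproduce.

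**Inputs from the documents.** Reference medians of 11.1 months (all afatinib patients) and 13.6 months (common mutations), protocol section 7. Dose-reduced share of 53%, section 7. Sample size of 200, section 9.5.

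**Assumptions, not in the documents.** Exponential times. Share *m* of observed progressions without any date: 2%, 5%, 10% or 20%. Exponential lag from progression to last contact with mean 0 to 12 months, cut off at the end of follow-up. Follow-up uniform over 6 to 33 months.

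**Step 1: how many patients.** With a median of 11.1, the hazard is λ = ln 2/11.1 = 0.0624 per month. The share of progressions observed is 1 − (e^(−6λ) − e^(−33λ))/(27λ) = 1 − (0.687 − 0.127)/1.686 ≈ 0.67, or about 134 of 200 patients. Missing shares of 2%, 5%, 10% and 20% are then about 3, 7, 13 and 27 patients.

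**Step 2: losing the event alone (lag 0).** The event hazard falls to (1 − m)λ, so the median becomes median/(1 − m). For 11.1:
- m = 2%: 11.1/0.98 = 11.33
- m = 5%: 11.1/0.95 = 11.68
- m = 10%: 11.1/0.90 = 12.33
- m = 20%: 11.1/0.80 = 13.87

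**Step 3: adding the lag.** Kaplan-Meier medians in months from large simulated samples. Each range runs from a mean lag of 0 to a mean lag of 12 months.

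| Undated share | Plan's rule, true 11.1 | Plan's rule, true 13.6 | Kept as event at last contact, true 11.1 |
|---|---|---|---|
| 2% | 11.3 to 11.4 | 13.9 to 14.0 | 11.1 to 11.3 |
| 5% | 11.7 to 11.9 | 14.3 to 14.5 | 11.1 to 11.5 |
| 10% | 12.3 to 12.8 | 15.1 to 15.6 | 11.1 to 11.9 |
| 20% | 13.9 to 15.0 | 17.0 to 18.3 | 11.1 to 12.7 |

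The shift is upward in every scenario, and most of it comes from losing the event. Extending follow-up to 36 months leaves the results almost unchanged. The last column shows that even the crudest alternative, an event dated at last contact, lies closer to the truth throughout.

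**Step 4: the dose-group comparison.** With a true hazard ratio of 1, the lag-0 approximation is (1 − m in reduced)/(1 − m in non-reduced). With 15% against 5% this is 0.85/0.95 = 0.89; reversed, it is 0.95/0.85 = 1.12. Simulation with 53% dose-reduced, mean lag 6 months and follow-up of 6 to 36 months gives about 0.87 and 1.13. With 10% in both groups it gives about 1.01.

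**Step 5: sampling error.** Ignoring censoring, the standard error of a median of 11.1 at n = 200 is √(0.25/200)/(0.5λ) = 0.0354/0.0312 ≈ 1.1 months.

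**The case against.** The strongest reply is that the rule may rarely matter. Because the SAP takes the earlier of two dates, it applies only when both are absent. The eCRF has automatic completeness checks (protocol section 9.8), and about 30% of patients have source verification. Neither document defines last contact. Section 9.3 ends documentation at last dose or the end of data collection, whichever comes first, so last contact may lie close to progression. The LUX-Lung 3 comparison is descriptive, and at 5% missing the shift of 0.6 to 0.8 months is smaller than one standard error. All of this stands, and it limits the size. It does not change the direction: checks cannot create a date that the chart lacks, and at zero lag the event is still lost.

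A reader might infer more than the text supports on four points.
- **Death:** that both documents censor undated deaths under this rule. Only the protocol's sentence mentions death.
- **Long lag:** that these patients stay event-free for years after progression. No lag or post-progression survival figure is given, so long-lag medians have no basis here.
- **Dose groups:** that the log-rank comparison is necessarily biased. It is nearly unaffected when missingness is equal.
- **Partial dates:** that a progression dated only to month or year is censored. Neither document says whether such a date counts as missing. That is a gap, not a stated rule.

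**Conclusion.** The point holds, with high confidence in the direction. For patients who stopped treatment with progression recorded and no date, the SAP and protocol discard a known event and bias the time-to-progression median upward. This is not a standard use of right-censoring.

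The size is conditional on quantities that the documents do not give. Under the assumptions above, a true median of 11.1 months is overstated by about 0.2 to 0.3 months at 2% missing, 0.6 to 0.8 at 5%, 1.2 to 1.7 at 10% and 2.8 to 3.9 at 20%. At 2% this is negligible beside sampling error. At 10% or more it could change how the result looks beside LUX-Lung 3. The between-group hazard ratio is at risk only if missingness differs by dose group, which the plan does not arrange to report.

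A related gap remains: no rule covers a patient still on treatment with recorded but undated progression. The point should be fixed before analysis, but it does not by itself undermine the study.

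**What to change.** In both SAP section 1 and protocol section 9.7.1:

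- Count a recorded progression as an event even when its date is missing or partial. Under the protocol's definition, do the same for a recorded death. Apply this whether or not the patient is still on treatment.
- Impute a partial date within the known month or year by a stated rule.
- For a fully missing date, treat the time as interval-censored between first dose (or a last progression-free date, if the eCRF captures one) and last contact. Alternatively, date the event at last contact as a conservative upper bound, with an earlier date such as last dose as a sensitivity analysis.
- Define last contact.
- Censor only patients with no recorded progression or death.
- Report the number of undated progressions by dose group, and keep the present rule only as a sensitivity analysis.

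The cost is wording in two documents, one or two extra analyses and a count. Dating at last contact, with last dose as the earlier date, needs only dates that the plan already uses. Tighter intervals would need an added field, because the data list in protocol section 9.3 has no last progression-free date, reason for stopping treatment or date of death. The downsides are that imputed dates carry some error, an interval starting at first dose is wide, and dating at last contact still overstates the median when the lag is long (up to 11.9 against a true 11.1 at 10% missing and a 12-month mean lag).
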